3.3.1 Rationale for Mircera Dose and Schedule

The completed Phase III program of Mircera in adult *patients with CKD* included four studies to assess how to switch patients treated with epoetin alfa, epoetin beta, or darbepoetin alfa to Mircera, administered intravenously or subcutaneously. The CFs that were tested in the Phase II Study NH19707 in pediatric patients were directly derived from the Sponsor's experience in adults receiving Mircera intravenously and from the results of a published study of darbepoetin alfa conducted in pediatric patients (Warady et al. 2006). This completed study identified CFs of $4 \times$ previous weekly darbepoetin alfa dose [μg]/0.55 for darbepoetin alfa and $4 \times$ previous weekly epoetin dose [IU]/125 for epoetin alfa and epoetin beta in order to switch from the previous weekly maintenance treatment dose to Mircera IV once every 4 weeks in HD patients. Model-based evaluation of the data from this pediatric study and subsequent simulations, coupled with the data from the adult studies, suggest that these CFs will also be appropriate in the SC setting. Real-world data from independent registries (International Pediatric Dialysis Network) of pediatric patients (3 months and older) treated with Mircera SC and IV confirmed the model-based simulations and the conversion factor identified in Study NH19707. Therefore, the same CFs will be used to identify the starting dose of Mircera administered subcutaneously every 4 weeks.

The patients included in this study are already on stable maintenance doses of SC ESA prior to conversion to Mircera and, assuming a linear relationship across dose ranges, the use of CFs will result in a Mircera dose that is proportional to the previous ESA dose, thus correcting for the higher weight-adjusted dose requirements in pediatric patients.

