6.7 PHARMACODYNAMIC ANALYSIS

Hb concentration-time data will be described, using non-linear mixed effect modeling. The previously developed PK/PD model was a life-span type of longitudinal model (Chanu et al. 2010). It will be updated with Study NH19708 data. The influence of covariates (e.g., previous ESA dose) on pharmacodynamic parameters will be studied.

Pharmacodynamic analysis will be performed in two steps:

- The existing pharmacodynamic model will be challenged against Study NH19708 data to check its predictive performance and to highlight any deviation from the current knowledge of Mircera PD properties.
- The PK/PD model will be updated by pooling Study NH19708 data with historical adult and pediatric pharmacodynamic data. Sensitivity analysis will be performed by re-estimating the PK/PD model parameters on pediatric data only.

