## **2.3 DETERMINATION OF SAMPLE SIZE**

This is an exploratory study without a powered statistical group comparison. Therefore, no formal sample size estimation will be performed; however, the calculations below indicate the approximate precision that could be achieved.

Assuming a 30% withdrawal rate (based on the withdrawal rate for the NH19707 study), of the 40 patients evaluable for ITT and safety analysis, more than 26 patients will have data for the evaluation period. Twenty-six patients will be sufficient to provide

approximately 90% power that the 90% CI for the Hb change from baseline to the evaluation period is between -1 and +1 g/dL, provided the standard deviation is smaller than 1.5 and the optimum dose conversion is able to maintain the Hb at the baseline level. This means that we assume there will be no change in the Hb levels from baseline to the evaluation period.

Approximately 10-15 of the patients will be < 12 years old, with the objective to include as many patients < 5 years old (minimum 3 patients) as possible. Approximately 10-15 patients, irrespective of their age, will not be on dialysis. Available HD patients receiving their ESA subcutaneously are eligible for enrollment. No more than 10 patients on HD should be enrolled.

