#### **4.3.1 Primary Efficacy Endpoint**

Hb concentration values (g/dL) over time and change in Hb from baseline to evaluation period will be presented in summary tables and graphically. The estimates will be summarized descriptively using means, standard deviation and percentiles.

The individual change from baseline will be reported using summary statistics (including mean, standard deviation and 90% CI of mean change). No formal statistical testing will be performed. Additional analysis will be performed by age category (<5, 5-11, ≥12 years), dialysis type (not yet on dialysis, PD, HD) and previous ESA (epoetin [epoetin alfa or epoetin beta or biosimilar] or darbepoetin alfa), if numbers allow.

The 90% confidence interval (CI) for the average per-patient Hb change from baseline to the evaluation period (weeks 17-21) will be calculated. If the lower limit of the CI is ≥-1 g/dL, the upper limit ≤1 g/dL and the number of dose increases and decreases are approximately balanced across the patients the conversion factor from prior ESA treatment for the first Mircera dose will be considered appropriate.

The Hb change from baseline is calculated on a per-patient basis, using an Area Under the Curve (AUC) approach to calculate an individual's average for both the baseline and evaluation periods and taking the difference. This per-patient change is then averaged over all patients and the confidence interval calculated.

The baseline period is defined as all assessments between the day of first study dose and the previous 35 days. If during the baseline period Hb measurements  $H_0, \dots, H_n$  are taken at timepoints  $t_0, \dots, t_n$ , a time adjusted average baseline Hb value will be calculated by

$$y = \frac{1}{2(t_n - t_0)} \sum_i (H_i + H_{i-1})(t_i - t_{i-1})$$

The value on the day of the first dose is included in the baseline calculation, as this assessment will be performed before the first dose is given.

The average Hb value for each individual during the evaluation period will be calculated using the same method as for the baseline period. The evaluation period is defined as all assessments between Visit 8 (Week 17) and Visit 10 (Week 21) inclusive. Subtracting the baseline period value from the evaluation period value gives the change in Hb concentration (g/dL) between the baseline and evaluation period.

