### **4.3.5 Subgroup Analyses**

The main subgroups used for analysis in this pediatric study will be the age groups (based on age at study start) used for stratification:

1. Age groups:
  - < 5 years
  - 5-11 years
  - $\geq$  12 years

Additionally, the other stratification factor that may be used for subgroup analyses:

2. Previous ESA treatment
  - epoetin alfa or epoetin beta or biosimilar
  - darbepoetin alfa
3. Dialysis type at study start
  - Not yet on dialysis
  - PD
  - HD

Analyses of the primary endpoint & the dose over time will be repeated by these subgroups.

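### The SAP 4.3.1 rule pools over prior ESA dose in both parts, so an offsetting departure from dose proportionality can be called appropriate, and no SAP analysis would show it

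*SAP*

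**What the plan says.** Protocol 4.3.2.1 (Table 2) assigns one of nine starting strengths from the previous weekly epoetin or darbepoetin dose. The premise is in Protocol 3.3.1: "assuming a linear relationship across dose ranges, the use of CFs will result in a Mircera dose that is proportional" to the previous ESA dose.

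SAP 4.3.1 states the rule for judging the factor. The first part is a confidence interval condition: "If the lower limit of the CI is ≥-1 g/dL, the upper limit ≤1 g/dL". It is computed on one pooled mean: "This per-patient change is then averaged over all patients and the confidence interval calculated". The second part is a condition on pooled counts, followed directly by what is being judged: "number of dose increases and decreases are approximately balanced across the patients the conversion factor from prior ESA treatment". No numerical bound is given for the second part, and neither part refers to prior dose.

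SAP 4.3.5 lists age group, ESA product and dialysis type, and says "Analyses of the primary endpoint & the dose over time will be repeated by these subgroups". SAP 4.3.2.2 summarises the ratio of the Week 1 to the Week 17 dose by mean, median, minimum and maximum. Prior dose level appears as an explanatory variable in one place, Protocol 6.7: "The influence of covariates (e.g., previous ESA dose) on pharmacodynamic parameters will be studied". SAP 2.2.4 places that modelling outside the SAP, and it does not enter the rule.

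**The concern.** The rule checks whether the conversion factor is right on average. It does not check whether the factor is right along the range of prior doses over which it is applied.

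Suppose the dose needed rises less than proportionally with prior dose. Children with low prior doses then start too low and children with high prior doses start too high. Titration raises the first group and lowers the second. Hb changes of opposite sign average towards zero, and the pooled counts of increases and decreases move towards equality, which is the pattern that the second condition rewards.

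At stake is what the trial may claim about its starting-dose table. A favourable result could be read as support for every band when it supports only the average over the children enrolled.

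**Working it through.** **1. The plan's own figure.** SAP 2.3 gives "approximately 90% power that the 90% CI for the Hb change from baseline to the evaluation period is between -1 and +1 g/dL" for n = 26, SD 1.5 and true change 0. The condition is |mean| + t(0.95, 25) × s/√26 ≤ 1. Simulating the mean and s gives 90.4%. The normal approximation 2Φ(√26/1.5 − 1.645) − 1 gives 92.1%. The figure is reproduced.

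**2. Size of a slope error.** The closed epoetin bands of Table 2 run from 1300 to 9500 IU/week, a ratio of 9500/1300 = 7.31. If need rises as (prior dose)^b, assigned/needed varies as (prior dose)^(1−b). Centred at the geometric mid-dose, it runs from 7.31^(−(1−b)/2) to 7.31^((1−b)/2):
- b = 0.8: 0.82 to 1.22
- b = 0.6: 0.67 to 1.49

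The documents give no value for b.

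**3. The CI part.** Let half the patients be shifted by −d and half by +d at evaluation. The mean is 0 and the SD is √(σ² + d²). With mean 0 and n = 26 the CI fails only if the observed SD exceeds √26/1.708 = 2.99 g/dL. Pass rates by simulation:

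| d (g/dL) | σ = 1.0 | σ = 1.5 |
|---|---|---|
| 0 | 99.9% | 90% |
| 0.5 | 99.8% | 88% |
| 1 | 98.9% | 81% |
| 1.5 | 94.3% | 65% |
| 2 | 75.9% | 40% |

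The means cancel but the added spread does not, so only large residual shifts are caught. Titration makes such shifts less likely: Mircera is given at Weeks 1, 5, 9, 13 and 17, with adjustment allowed at each dosing day after the first.

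**4. Both parts together.** This titration simulation (n = 28, 400 trials per setting) is illustrative. Its assumptions are not in the documents: log-normal prior dose with median 3500 IU/week and log-SD 0.7; 1.5 g/dL per dose doubling; one syringe step per adjustment; balanced meaning that one third to two thirds of changes are increases. Here δ is the power of prior dose by which assigned/needed grows (δ = 1 − b), and the crossing point is where assigned equals needed.

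| δ | Crossing point | CI part | Both parts | Increases / decreases | Increases as share of changes, low / high half |
|---|---|---|---|---|---|
| 0 | – | 100% | 80% | 11.6 / 9.9 | 58% / 50% |
| 0.3 | median | 100% | 80% | 13.2 / 12.8 | 73% / 28% |
| 0.5 | median | 100% | 81% | 16.1 / 15.2 | 82% / 19% |
| 0.5 | 2 × median | 100% | 1.5% | 34.5 / 5.2 | 97% / 65% |
| 0.5 | ½ × median | 100% | 2.5% | 6.0 / 33.5 | 42% / 3% |
| 0.3 | 2 × median | 100% | 12% | 23.1 / 6.1 | 91% / 60% |

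The Monte Carlo standard error near 80% is √(0.8 × 0.2/400) = 2 points, so 80% and 81% are indistinguishable. The simulated SD of Hb change was 0.52 to 0.57 g/dL, well below the plan's 1.5, so the 100% for the CI part is optimistic. The split by prior dose is what separates the centred error from no error. Mean Hb change does so only weakly (−0.16 and +0.19 g/dL in the two halves at δ = 0.5), because titration has largely corrected it.

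**The case against.** A reader might infer that the rule cannot detect a slope error at all. The documents do not support that. Cancellation in the counts needs the error to cross near the middle of the enrolled prior doses, and neither document gives their distribution. Off centre, the balance part usually tips, as step 4 shows. What remains is that the result would then look like a uniform level error, although a uniform change to the factor would not remove a slope error.

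The simulated pass rates are not properties of the SAP rule, because its balance criterion has no bound. A separate simulation, reading it as 40–60% increases, passed a correct factor in 57% of trials and slope errors in 57–59%. The level depends on the reading. The near-equality with and without a centred slope error appears under both.

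A mild error is no larger than Table 2 rounding. In the 1300 to <2000 IU/week band, 4 × dose/125 gives 41.6 to 64 µg against 50 µg assigned, a ratio of 1.20 down to 0.78, similar to the whole-range drift at b = 0.8. This stands for b = 0.8. Rounding, however, recurs within each band and does not accumulate along the range.

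Protocol 3.3.1 also cites model-based evaluation, simulations and registry data, so proportionality is not the factor's only support. The PK/PD model may examine prior dose, and the by-age results or the extremes of the dose ratio may hint at a pattern. None of these enters the rule, and none is a SAP output by prior dose.

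**Conclusion.** The point holds as a gap in the rule. Both parts pool over the variable that sets the starting dose, and the SAP has no analysis by that variable. A departure from proportionality centred on the enrolled doses can therefore be declared appropriate about as often as a correct factor: 81% against 80% at exponent 0.5, under the assumptions in step 4.

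The size rests on an assumed prior-dose distribution, Hb response, titration step and balance bound. A reader might go further and infer that the starting-dose table is biased at its ends. Nothing in the documents shows that. They show only that the planned rule would not reliably reveal it. The change is worth making because the stated objective is to ascertain the starting dose and the data needed are already collected.

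**What to change.** Add to SAP 4.3.1 and 4.3.5:

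1. A table by low, middle and high Table 2 band showing Hb change, the Week 17/Week 1 dose ratio, and the numbers of increases and decreases.
2. A regression of ln(Week 17/Week 1 dose) on ln(prior weekly ESA dose). Put both products on one scale with the protocol's own factors (4 × dose/125 for epoetin, 4 × dose/0.55 for darbepoetin). Fit it in the closed bands, because the end strengths distort the slope. Report the slope with a 90% CI. With complete titration the slope estimates b − 1.
3. A sentence stating that the pooled rule supports the conversion factor on average over the enrolled doses, and that any statement across the dose range is to be read with the slope, its CI and the band table.

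Do not make an interval that includes 0 a condition for calling the factor appropriate. That would treat non-significance as proof of proportionality. In a simulation with 28 patients (assumed 2.5 g/dL per unit of ln dose and an 8-week lag), a one-sided 5% slope test flagged 25% of trials at exponent 0.8 and 64% at 0.6, so 75% and 36% would have passed. A gate would also sit badly with an exploratory study that plans no formal testing.

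The cost is one table and one model, with no new data. Precision is limited at about 26 to 28 evaluable patients, and fewer in the closed bands. Chance-high screening doses can produce a mild negative slope, which the report should say. No dose or dosing rule is proposed.

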3.3 RATIONALE FOR STUDY DESIGN

Most patients with CKD undergoing HD or PD require continuous long-term treatment with ESAs to correct anemia and to maintain anemia correction. The Sponsor has completed Phase II and III studies of Mircerca and has shown that it is safe and effective in the treatment of anemia in adult patients *with CKD* not yet on dialysis and in those patients receiving HD or PD. Furthermore, Study NH19707 has shown that pediatric patients with CKD on HD can be safely and effectively switched from maintenance

treatment with IV epoetin alfa, epoetin beta, or darbepoetin alfa to Mircera IV using CFs to define the starting dose. The purpose of this study is to use the same CFs to ascertain the starting dose of Mircera given subcutaneously for the maintenance treatment of anemia with SC ESAs in pediatric patients with CKD on dialysis or not yet on dialysis.

The study design is based on the study design of NH19707 but with fewer visits, as patients on PD or not yet on dialysis visit the nephrology centers less frequently than patients on HD. The similar study design will allow pooling of the data from the two pediatric studies.

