## **3. STUDY CONDUCT**

### **3.1 RANDOMIZATION**

Patients will be enrolled to receive Mircera once every 4 weeks, and no randomization will be performed. An interactive voice or Web-based response system (IxRS) will be used to track the enrollment and to monitor the disposition of patients with respect to the different subgroups (age group and dialysis type).

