### **3.2 DATA MONITORING**

The IMC reviewed the general safety and efficacy of Mircera in this patient population as well as PK data on 12 September 2019, after 12 subjects completed the core study period (20 weeks of treatment). The IMC consisted of representative(s) from Clinical Science, Drug Safety, Clinical Pharmacology and Biostatistics. The main purpose of the IMC was to assess if the conversion factor from the previous ESA dose to give the starting dose of Mircera SC is appropriate to maintain stable hemoglobin (Hb). The SMT

was recommended to plan and prepare for this interim analysis. The SMT Statistician and the Statistical Programming Analyst performed the interim analyses. Based on the review of the data and the meeting discussion, the IMC recommended to continue the study unchanged. The Development Review Committee (DRC) chair, on behalf of the study team, accepted the IMC recommendations. For detailed description of the role and process of the IMC, please refer to the IMC Agreement.

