#### **4.6 INTERIM ANALYSES**

Once 12 patients have completed 20 weeks of treatment, an interim analysis to assess efficacy, safety, and pharmacokinetics was performed. The analysis was reviewed by a Roche Internal Monitoring Committee (IMC) with the primary objective of assessing the safety and efficacy of the CFs for starting treatment with SC Mircera. This was assessed using Hb (the pharmacodynamic marker), changes in dose, and assessment of the PK data to compare to the available pediatric PK data under IV dosing. The variability of Hb was also assessed at this time, with regards to protocol assumptions.

An individual's Hb response was based on the mean Hb during the evaluation period (Weeks 17-21) and is defined as a mean Hb change from baseline within  $\pm 1\text{g/dL}$ . The 90% CI for the average Hb change from baseline was calculated.

The full details of the interim analysis and any decision criteria have been specified in separate IMC documents. The statistical analysis has been detailed in a separate Interim analysis SAP.

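### SAP 4.3.1 gives one pooled verdict for two conversion factors, so opposite errors in the epoetin and darbepoetin groups can offset unless the conclusion is worded for each factor

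*SAP*

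**What the plan says.** Protocol 1.3 and 3.3.1 take two factors from Study NH19707: 4 × weekly epoetin dose (IU)/125 and 4 × weekly darbepoetin dose (µg)/0.55. Protocol 3.3.1 carries both over: "Therefore, the same CFs will be used to identify the starting dose of Mircera administered subcutaneously every 4 weeks". Table 2 in Protocol 4.3.2.1 has a separate column for each prior ESA.

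The only rule for the verdict in the final-analysis SAP is in section 4.3.1. It has two parts: the 90% CI of the per-patient Hb change, averaged over all patients, must lie within ±1 g/dL, and dose increases and decreases must be "approximately balanced across the patients the conversion factor from prior ESA treatment for the first Mircera dose will be considered appropriate". The factor is in the singular, both parts are pooled, and the balance has no numeric limit.

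Prior ESA is not ignored. SAP 4.3.1 plans the primary endpoint by prior ESA, conditional on numbers. SAP 4.3.5 says that analyses of the primary endpoint and "the dose over time will be repeated by these subgroups", yet it introduces prior ESA under "the other stratification factor that may be used for subgroup analyses". SAP 4.3.2.2 and 4.3.2.4, on dose change, name only overall and by-age summaries. No section links a by-ESA result to the verdict.

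**The concern.** The efficacy objective is to ascertain the starting dose, and that dose comes from one of two factors according to prior ESA. Suppose one factor starts patients too high and the other too low. The first group then contributes dose decreases and upward Hb shifts, the second increases and downward shifts. In the pooled mean and the pooled count these cancel, and the rule calls *the* factor appropriate when neither is.

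The Hb part gives limited protection even without pooling. It uses Hb at Weeks 17–21, after Protocol 4.3.2.1.1 has allowed adjustment towards baseline at Weeks 5, 9 and 13. It therefore mainly shows that Hb is maintained under titration. Evidence on the starting dose lies largely in the dose changes, which makes pooling of the balance part the more important weakness.

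**Working it through.** **The plan's own figure.** Inputs from Protocol 6.1 and SAP 2.3: n = 26, SD 1.5, true change 0, 90% CI within ±1 g/dL. Power is P(|mean| + t(0.95, n−1) × s/√n ≤ 1), integrated over the sample SD s. The result is 90.3%, against the stated approximately 90%. With 30% withdrawal, 40 × 0.7 = 28, consistent with more than 26. The sample size statement is sound for the pooled CI.

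**Offsetting in the Hb part.** Assumed, because no document gives them: 13 patients per group and group mean changes of −1 and +1 g/dL. Overall SD is held at 1.5.
- Pooled mean: (13 × (−1) + 13 × 1)/26 = 0.
- Pooled half-width: 1.708 × 1.5/√26 = 0.50. CI −0.50 to +0.50: **passes**.
- Within-group SD: √[(25 × 1.5² − 26 × 1²)/24] = √(30.25/24) = 1.123.
- Group half-width: 1.782 × 1.123/√13 = 0.555. CIs −1.55 to −0.45 and +0.45 to +1.55: **both fail**.

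If the within-group SD is itself 1.5, the overall SD is √[(24 × 2.25 + 26)/25] = 1.789. The pooled CI is then −0.60 to +0.60 and still passes.

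**How often the pooled Hb part passes** (simulation, 60,000 trials per case, true changes −1 and +1 g/dL):

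| Split | Within-group SD 1.0 | Within-group SD 1.5 |
|---|---|---|
| 13/13 | 99% | 81% |
| 10/16 | 93% | 70% |
| 6/20 | about 55% | about 35% |

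The fall with imbalance follows from the pooled mean: 0 at 13/13, (16 − 10)/26 = 0.23 at 10/16, and (20 − 6)/26 = 0.54 at 6/20.

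**Offsetting in the balance part.** If one group has k decreases and the other k increases, the pooled count is k to k, which is balanced on any definition. If both factors err in the same direction, changes go predominantly one way and the balance part should object. The gap is therefore specific to opposite errors.

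**What separate groups can support.** Applying the ±1 CI to each group, with true change 0 and 13/13:
- SD 1.5: about 47% power per group, about 22% that both pass.
- SD 1.0: about 92% per group, about 85% that both pass.

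At SD 1.5, 90% power per group needs 26 evaluable in each (52 in all; 52/0.7 gives 75 enrolled). A 90% chance that both pass needs 31 in each (62; 62/0.7 gives 89 enrolled).

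**The case against.** The strongest reply is that the planned output would already reveal an offset. SAP 4.3.5 repeats the primary endpoint and dose over time by subgroup, and prior ESA is on the list. On a fair reading that extends the dose ratio and dose-change counts of SAP 4.3.2.2 to prior ESA. This largely stands: a reader might infer that the SAP ignores prior ESA, and it does not. What remains is the optional wording and the absence of any route from those tables to the conclusion.

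Second, the study is exploratory, has no formal testing, and had an interim review. "The main purpose of the IMC was to assess if the conversion factor from the previous ESA dose to give the starting dose" of SC Mircera was appropriate (SAP 3.2), and that review advised continuing unchanged. "The full details of the interim analysis and any decision criteria have been specified in separate IMC documents", so criteria by prior ESA may exist there. This limits the operational stakes. It does not alter the final rule, which still commits to a verdict.

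Third, opposite errors are hypothetical. The factors imply 125/0.55 = 227 IU epoetin per µg darbepoetin. Opposite twofold errors would need a true ratio of about 57 or 909, a fourfold relative error that nothing in the documents supports. NH19707 concerned switching from maintenance "treatment with IV epoetin alfa, epoetin beta, or darbepoetin alfa to Mircera IV using CFs to define the starting dose", so a reader might infer that the factors are untested for SC use. But Protocol 1.3 and 3.3.1 cite adult experience, simulations, and registry data in children treated SC and IV. An error in Mircera's SC bioavailability would also affect both groups in the same direction. These points stand. Against them, Protocol 1.3 still lists SC use and confirmation of the modelling among the open questions.

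Fourth, binding pass/fail limits per group would be a poor remedy at this sample size. That also stands, and none is proposed.

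**Conclusion.** The concern holds as a gap in the decision rule. Two factors are in use, one pooled verdict is given, and both parts of the rule can be met by opposite errors. Followed as written, the rule could call both factors appropriate when neither is.

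The size is minor to moderate. Masking is strong when the groups are of similar size and weakens as the split becomes uneven. The split is unknown: under SAP 3.1 the enrolment system tracks age group and dialysis type, not prior ESA. The percentages above cover the Hb part only and rest on assumed splits and SDs and on ±1 g/dL shifts. Shifts that large are a strong scenario after 16 weeks of titration; smaller conversion errors would show mainly in dose changes. The figures show what the rule permits and do not estimate this trial's risk.

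A reader might infer that the trial is likely to endorse wrong factors, or that its sample size is wrong. The documents support neither: nothing shows that opposite errors exist, and the stated power reproduces.

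**What to change.** Before database lock:

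1. In SAP 4.3.1 and 4.3.5, make the prior-ESA split (epoetin, darbepoetin) definite by removing the condition on numbers and the permissive wording for this factor.
2. For each group report the mean Hb change with 90% CI, the numbers of dose increases and decreases, and the geometric mean Week 17/starting dose ratio with 90% CI. The geometric mean treats halving and doubling alike: ratios of 0.5 and 2 have arithmetic mean 1.25 and geometric mean √(0.5 × 2) = 1. State how a withheld Week 17 dose enters the ratio. Table 3 stops doses only for high and rising Hb, so dropping such patients would favour a factor that starts too high.
3. Keep the pooled rule as the overall criterion. Say that its Hb part shows Hb maintained under the dose-adjustment rules. Word the conclusion separately for each factor from its own group's Hb change and dose changes. If the groups point in opposite directions, call neither factor appropriate on the pooled result alone.

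The cost is SAP wording and a few tables from data already collected; no dose or titration rule changes. The downside is imprecision within groups, so a group that misses should be reported as not shown rather than wrong, with no new binding per-group limit.

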###### **4.1.2 Per Protocol Population**

The Per-Protocol (PP) population is defined as all patients included in the safety population and who have no major protocol deviations as defined below.

1. Patients with less than 3 Hb values during the evaluation period.
2. Patients who miss any application of study medication at week 13 or week 17.
3. Patients with an overdose of Mircera at week 17 captured as a protocol deviation
4. Patient with wrong Mircera starting dose
5. Patients who do not fulfill the inclusion criteria for:
  - hemoglobin
  - iron levels
  - stable dose and dosing interval of SC treatment with epoetin alfa, epoetin beta or biosimilars, or darbepoetin alfa
6. Patients who fulfill any of the exclusion criteria:
  - Hemolytic anemia
  - Use of prohibited therapy

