For patients with no recorded Hb during the evaluation period, the primary endpoint will be missing. Values missing in between non-missing assessments will not be replaced or imputed. To correct for any increase in Hb caused by RBC transfusions, the Hb values measured within 3 weeks after an RBC transfusion will be deleted.

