#### **4.3.2 Secondary Efficacy Endpoints**

##### **4.3.2.1 Number of patients within stable range of Hb**

The number of patients with an average Hb concentration during the evaluation period within  $\pm 1$  g/dL of their baseline Hb or above, within, or below the range of 10-12 g/dL and those who fulfill both criteria will be summarized. The classification of each patient will be based on their average Hb for the baseline and evaluation periods as calculated for the primary endpoint.

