### **4.3.4 Sensitivity Analyses**

Sensitivity analysis may be carried out for the primary efficacy endpoint based on the number of patients who do not respond to increasing doses of Mircera over the study duration. Sensitivity analysis for data exploration may also be done for the primary efficacy endpoint if a large volume of data is missing.

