#### **4.5 MISSING DATA**

For patients with no recorded Hb during the evaluation period, the primary endpoint will be missing. Values missing in between non-missing assessments will not be replaced. To correct for any increase in Hb caused by RBC transfusions, the Hb values measured within 3 weeks after an RBC transfusion will be deleted.

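### Is the primary endpoint left undefined when only one evaluation-period Hb survives the transfusion rule?

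*SAP*

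**What the plan says.** SAP 4.3.1 defines each patient's average as a sum of trapezoids divided by 2(t_n − t_0) and uses the same method for baseline and evaluation. On the window: "The evaluation period is defined as all assessments between Visit 8 (Week 17) and Visit 10 (Week 21) inclusive". The schedule (Protocol Appendix 1, SAP Appendix 2) places Hb samples in that window at Weeks 17, 19 and 21.

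Three rules deal with absent values:
- After transfusion, "the Hb values measured within 3 weeks after an RBC transfusion will be deleted".
- With nothing left: "For patients with no recorded Hb during the evaluation period, the primary endpoint will be missing".
- For interior gaps (SAP 4.5): "Values missing in between non-missing assessments will not be replaced". Protocol 6.4.1 explains that the trapezoid interpolates across them.

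Exactly one remaining value is not mentioned in SAP 2.2.1, 4.3.1 or 4.5, nor in Protocol 6.4.1. A minimum count exists only for the per-protocol set, where SAP 4.1.2 lists as a major deviation "Patients with less than 3 Hb values during the evaluation period". The primary analysis is on ITT.

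The secondary counts in SAP 4.3.2.1 inherit the same average: "The classification of each patient will be based on their average Hb for the baseline and evaluation periods as calculated for the primary endpoint". Sensitivity analyses in SAP 4.3.4 are optional. One is "based on the number of patients who do not respond to increasing doses of Mircera over the study duration"; for the other, "Sensitivity analysis for data exploration may also be done for the primary efficacy endpoint if a large volume of data is missing".

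**The concern.** With one value the sum has no terms and the divisor is zero, so the formula returns 0/0. The plan's own deletion rule can produce this, because its 21 days exceed the 14-day sampling gap. Missed visits can do the same, as can a kidney transplant soon after Week 17, since Protocol 4.6.2 provides no follow-up visit unless it precedes the transplant.

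A program that applies the formula literally would drop such a patient from the primary mean and from the stable-range counts. The loss would not be random: it would fall on patients transfused during, or just before, the period used to judge the conversion factor. The study is open label, so a convention chosen late would be chosen with outcomes visible. Neither trigger in SAP 4.3.4 is aimed at one or two transfused patients.

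**Working it through.** **Inputs.** From the documents: margins ±1 g/dL, 90% CI, SD 1.5 as the upper bound, true change 0, 26 patients for about 90% power, 40 enrolled with 30% withdrawal (SAP 2.3); deletion window 21 days (SAP 4.3.1); visit window ±3 days (Protocol Appendix 1). The documents give no transfusion rate and no expected Hb in transfused patients, so those are assumed below.

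**The plan's own figure.** The probability that |mean| + t(0.95, n−1)·s/√n ≤ 1, averaged over the sampling distribution of s, is 0.903 at n = 26. This reproduces the stated 90%. Expected evaluable patients: 40 × 0.70 = 28.

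**The formula at one value.** Numerator 0, divisor 2(t_0 − t_0) = 0, hence 0/0. If Hb is constant at H over any interval, however short, the formula returns H. The natural extension to one value is therefore y = H.

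**When one transfusion leaves one value.** With the first dose on Day 1, the nominal visits fall on Days 113, 127 and 141. A value is deleted if it falls 1 to 21 days after the transfusion.
- Transfusion on Days 106–112 (7 days) deletes Weeks 17 and 19 and leaves Week 21.
- Transfusion on Days 120–126 (7 days) deletes Weeks 19 and 21 and leaves Week 17. The pre-transfusion Hb required by Protocol 4.4.3 also falls inside the window; if it counts as an assessment, two values remain.
- Over the visit windows, the Visit 8 to Visit 9 gap is 8 to 20 days, so the first interval lasts 21 − 20 = 1 to 21 − 8 = 13 days.
- Visits 8 and 10 are at least 28 − 6 = 22 days apart, so one transfusion cannot delete all three values.

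Seven days is 7/140 = 5% of treatment days. That is the share of days on which a transfusion would matter, not a risk per patient. If 5% to 20% of patients had one transfusion, uniform over 140 days, the expected number of one-value patients among 28 would run from 28 × 0.05 × 7/140 = 0.07 to 28 × 0.20 × 14/140 = 0.56.

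**Effect on the primary result.** Take baseline 11 g/dL, single value w, and the other 27 patients averaging 0. Using rather than dropping the value shifts the mean by |w − 11|/28:

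| w (g/dL) | shift (g/dL) | share of room |
|---|---|---|
| 11.0 | 0 | 0% |
| 10.5 | 0.018 | 3.5% |
| 9.5 | 0.054 | 10.4% |

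The room is 1 minus the half-width t(0.95, 27) × 1.5/√28 = 0.483, that is 0.517.

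**Effect on the CI** (n = 28, other patients mean 0 and SD 1.5):

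| One-value patients | Change (g/dL) | 90% CI, included | 90% CI, excluded |
|---|---|---|---|
| 1 | −1 | −0.51 to 0.44 | −0.49 to 0.49 |
| 1 | −3 | −0.62 to 0.40 | −0.49 to 0.49 |
| 2 | −3 | −0.74 to 0.32 | −0.50 to 0.50 |

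All lie within ±1. If such patients were dropped, power would go from 0.903 at n = 26 to 0.889 at 25 and 0.872 at 24.

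**Effect on the stable-range count.** One patient is 1/40 = 2.5 to 1/28 = 3.6 percentage points.

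**The case for a change.** The strongest case for acting is that a primary endpoint should be computable for every patient who has data, that the affected patients are not a random subset, and that one sentence would settle it. The per-protocol count does not help the ITT analysis, and the sensible convention is nowhere written. All of that is true.

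It does not follow that the plan excludes these patients. The SAP reserves the missing status for patients with no recorded Hb; dropping someone with one usable value would go against that text. A division by zero also shows up in programming, and evaluation-period Hb is listed for every patient under SAP 4.3.2.3, so a lost patient would be seen.

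It may also be objected that a single later value can make a patient transfused for worsening anemia look stable. That comes from the deletion rule, not from the one-value case: a patient with two remaining values has the same issue. Adding a one-value rule would not remove it. Carrying the pre-transfusion Hb through the deletion window is a debatable imputation. It treats the lowest value as lasting three weeks, even after acute blood loss, which Protocol 4.3.2.1.2 separates from poor response. Nor is it clear that deleted values appear nowhere: SAP 4.4.3 plans a time-adjusted evaluation average for Hb without restating the deletion, although SAP 4.5 could be read as applying it there too.

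Two further ambiguities have natural readings. A pre-transfusion Hb taken between Visits 8 and 10 is among all assessments in the period, unless it falls within three weeks after an earlier transfusion. An early-withdrawal visit before Week 17 lies outside the period, which SAP 4.3.1 ties to Weeks 17 to 21 even though Protocol 4.6.2 uses the Visit 10 assessments for it.

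**Conclusion.** The algebra holds and the SAP has no one-value rule, but this is a gap that an analyst fills sensibly by using the single value. The choice is worth 0.018 g/dL in the mean (0 to 0.054 over the assumed values) against room of about 0.52, and about 1.5 points of power per patient if the patient were dropped. The ±1 g/dL criterion holds in every illustrated case, including two patients at −3 g/dL. These sizes assume 28 evaluable patients, SD 1.5, the other patients averaging zero change, and at most two one-value patients. The room would shrink if the overall mean were already well away from zero. The study is exploratory with no formal testing, and the conversion-factor judgement also weighs the balance of dose changes. No change to the plan is needed.
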